11.6 SAFETY ANALYSES

11.6.1 Adverse Events

All AEs will be coded using the MedDRA dictionary using the version specified in the Data Management Plan (DMP).

All AEs, including those which occurred prior to the first dose of study drug, will be listed. Only treatment emergent adverse events (TEAEs), i.e., existing conditions that worsen or events that occur during the course of the study after administration of IMP, will be included within the summary tables. TEAEs will be summarised by dose group, age group and overall.

An overall summary of AEs will be produced including the number of TEAEs; the number and % of subjects reporting at least 1 TEAE, serious TEAE (where SAE is reported as 'Yes'), TEAE leading to withdrawal from study drug (Action recorded as 'Study Drug Discontinued'); the number and % of subjects reporting TEAEs by severity and relationship to study drug. A subject with multiple occurrences of any AE is counted only once at the maximum level of severity or the highest association to study drug.

The number of TEAEs and the number and % of subjects reporting at least one TEAE will be tabulated by system organ class (SOC) and preferred term (PT). A subject reporting multiple episodes of a particular AE will only contribute one count towards the corresponding SOC and preferred term. The number of TEAEs and the number and % of subjects reporting at least one TEAE will also be tabulated by preferred term (PT), with the PTs sorted in descending order of frequency. A subject reporting multiple episodes of a particular AE will only contribute one count towards the corresponding PT.

In addition, the number and % of subjects reporting TEAEs will be tabulated by maximum severity and strongest relationship to study drug. For the summary of TEAEs by severity, if a subject has multiple events occurring within the same SOC or preferred term the event with the highest severity will be counted. Similarly, for TEAEs by relationship to study drug, if a subject has multiple events occurring within the same SOC or PT, the event with the highest association to study drug will be counted.

Data will be listed by dose group and age group. For any adverse event taken prior to first administration of study drug, treatment will be described as 'Prior to Dosing'.

Where there are only partial dates/times recorded for adverse events, adverse events will be assigned to treatment unless it can be ruled out based on the partial information.

The derived variables, 'Time from Dose' and 'Duration' will be presented where full date and time are present. If partial dates are present for any parameter required in the calculation, then the variable will not be populated. The following will be used to calculate the variables:

Duration (dd:hh:mm): (Date/Time of Resolution-Date/Time of Onset) + 1 minute;

Time from Dose (dd:hh:mm): (Date/Time of Onset-Date/Time of Start of Dose).

The following will be presented in listing format within the data summaries:

Serious Adverse Events – If there are none present, the listing will be produced stating: ‘No subjects experienced any serious adverse events’.

Adverse Events which Led to Withdrawal of Study Drug – If there are none present, the listing will be produced stating: ‘No subjects experienced any adverse events that led to withdrawal of study drug’.

Adverse event data will be summarised and listed using the Safety Set.

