### 2.2. Cytisine

[figure not shown]
(-)-Cytisine, a plant-based alkaloid isolated from seeds of *Cytisus laburnum* (Golden rain acacia), has been used as a smoking cessation drug since the 1960's in Eastern and Central Europe, marketed as [REDACTED]. Despite its widespread use, cytisine has not been clinically developed outside of [REDACTED] Eastern and Central European territories. Achieve Life Sciences has acquired the license to cytisine outside of [REDACTED] territories to pursue clinical development and market approvals. There is widespread support for this strategy from leaders in the field.

[REDACTED] focus on clinical development of cytisine was in its traditional markets in Eastern and Central European countries where the initial clinical studies were conducted and published, but not in English. Because most of the clinical development trials leading to market approval in these countries occurred decades ago, the trials were not performed according to today's standard Good Clinical Practice (GCP) guidelines. Cytisine has been more recently evaluated in newer clinical trials, including additional pharmacokinetic (PK) studies and two large randomised Phase 3 clinical trials that were conducted according to GCP with more than 2,000 participants. The overall objectives in these more recent trials were to confirm the PK, efficacy, and safety of cytisine according to current clinical development standards. This clinical trial is being conducted to assess the pharmacokinetic parameters in far greater detail than has been reported for the commercial dose schedule as well as assessing a higher dose, as recommended by FDA for a future Phase 3 trial.

As a smoking cessation treatment using cytisine, the designated number of 1.5 mg cytisine tablets to achieve a particular dose or schedule are taken orally with approximately 240 mL of

water. The marketed dosing (1.5 mg tablet) and timing schedule for [REDACTED] are shown in Figure 1.

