## **8.9. Dose Modifications for 3.0 mg Dose or Elderly Subjects (>65)**

Dose modifications should not be necessary, unless a severe adverse event warrants holding or missing a dose as outlined below during the first 1 – 16 days in the 3 mg cytisine dosage group or at any time in elderly subjects.

Cytisine at higher levels in toxicology studies elicited adverse reactions primarily on the gastrointestinal system such as vomiting or diarrhea. Based on the HED calculations in newly conducted GLP toxicology studies (see Section 2.5), the safety margin supports the 3 mg dose (maximum of 18 mg for the first 3 days). The commercial dose of 1.5 mg (maximum of 9 mg for the first 3 days) has been well tolerated with no or minimal gastrointestinal symptoms. However, if a subject has nausea that results in vomiting or has minimal diarrhea progressing to severe diarrhea, the Principal Investigator/Sponsor Medical Monitor can delay, hold or skip doses. Dosing should resume within 48 hours when the adverse event has subsided to a moderate grade (see Table 8) or minimal symptoms. Dosing should then resume on the same schedule without modification. If the adverse event has not subsided to at least a moderate grade within 48 hours, the subject should be withdrawn from further study treatment.

For all subjects randomised to the 3.0 mg dosing schedule, if a severe adverse event reoccurs during the Day 1-16 dosing, then dosing should be again held until the adverse event has subsided to a moderate grade or minimal symptoms within a 48-hour period. Dosing should then be reduced as specified in Table 5. If the severe adverse event reoccurs after reducing the dose, the subject should be withdrawn from further study treatment. If the severe adverse event does not reoccur, the patient can continue the study treatment with dosing at the 1.5 mg level as shown in Table 5.

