**Table 5: Dose Modification for 3.0 mg Dose Group**

Days	Regimen	Total Daily Dose	Dose Modifications After Recurrence
1-3	6 times daily	18.0 mg	9 mg total daily dose (Reduce to one 1.5 mg cytisine tablet 6 times daily and follow the remaining schedule as for the 1.5 mg dosing group).
4-12	5 times daily	15.0 mg	7.5 mg total daily dose (Reduce to one 1.5 mg cytisine tablet 5 times daily and follow the remaining schedule as for the 1.5 mg dosing group).
13-16	4 times daily	12.0 mg	6 mg total daily dose (Reduce to one 1.5 mg cytisine tablet 4 times daily and follow the remaining schedule as for the 1.5 mg dosing group).
17-20	3 times daily	9.0 mg	No dose modification
21-24	2 times daily	6.0 mg	No dose modification
25	Once daily	3.0 mg	No dose modification

For elderly subjects in the 1.5 mg dosing schedule, if a severe adverse event reoccurs at any time, then dosing should be held until the adverse event has subsided to a moderate grade or minimal symptoms within a 48-hour period. Dosing should then be reduced by one dose per day. If the severity of the event then reoccurs, the subject should be withdrawn from further study treatment.

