6.2 PK SET

The PK Set will include all subjects who have completed all cytisine dosing on Days 1-3, completed >90% cytisine dosing on Days 4-25 and comply with the following criteria:

- Do not have an occurrence of vomiting or severe diarrhoea which renders the concentration profile unreliable (i.e. vomiting occurring at or before 2 times median T_{max});
- Do not use a concomitant medication which renders the concentration profile unreliable;
- Have at least one evaluable concentration that is preceded by a lower evaluable concentration and followed by a lower evaluable concentration for the calculation of C_{max} , T_{max} and AUCs (i.e. at least 3 evaluable concentrations in total);
- Do not violate the protocol (major protocol deviation) in a way that may invalidate or bias the PK results.

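### The named adverse-event tables count withdrawals but not dose holds or reductions, although Protocol 8.9 writes a reduction step for only 24 of the 36 planned subjects

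*SAP*

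**What the plan says.** **Objective.** SAP section 2 and Protocol 4.2 make the comparison of PK and tolerability between 1.5 mg and 3.0 mg, at ages 18-65 and over 65, a secondary objective. Protocol 2.2 describes the trial as "assessing a higher dose, as recommended by FDA for a future Phase 3 trial".

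**Tabulation.** The overall summary in SAP 11.6.1 counts subjects with any TEAE, a serious TEAE, a "TEAE leading to withdrawal from study drug" (identified by the discontinuation code under action taken), and TEAEs by severity and relationship. Summaries are by dose group, age group and overall. Table 14.3.1.7, in listing format, covers withdrawal again. No AE table title in SAP 14.3.1 mentions a hold or a reduction.

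**Dosing rules (Protocol 8.9).**
- The opening sentence foresees modification for a severe event on Days 1-16 "in the 3 mg cytisine dosage group or at any time in elderly subjects".
- The paragraph on delaying, holding or skipping doses for vomiting or severe diarrhoea is worded for any subject.
- For 3.0 mg, if a severe event recurs on Days 1-16, "then dosing should be again held until the adverse event has subsided to a moderate grade". The dose is then cut to 1.5 mg as in Table 5. "If the severe adverse event does not reoccur, the patient can continue the study treatment with dosing at the 1.5 mg level". "If the severe adverse event reoccurs after reducing the dose, the subject should be withdrawn from further study treatment".
- For elderly subjects on 1.5 mg, a recurrent severe event at any time leads to a further hold. "Dosing should then be reduced by one dose per day". Withdrawal follows if the event comes back.
- For subjects aged 18-65 on 1.5 mg, no reduction step is written.

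**The concern.** Withdrawal is a fair tolerability measure across groups when subjects have similar ways of staying on drug. Here they do not. Some subjects have a lower dose available before withdrawal and others have no such step in writing.

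The result most at risk is the one a dose-selection reader wants: how many subjects could stay on 3.0 mg. Someone who fails 3.0 mg twice and finishes at 1.5 mg is absent from the withdrawal row. Under SAP 11.1 that person can also, quite properly, be counted as completing the study. No table named in the SAP states how many such subjects there were. A reader of the withdrawal row alone would not learn that the groups were managed under different rules.

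**Working it through.** **1. Who has a written reduction step.** SAP 3.6 plans 12 non-elderly and 6 elderly subjects per dose group.

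| Cell | n | Reduction step in Protocol 8.9 |
|---|---|---|
| 3.0 mg, 18-65 | 12 | Half dose, Days 1-16 |
| 3.0 mg, >65 | 6 | Half dose, Days 1-16 |
| 1.5 mg, >65 | 6 | One dose per day fewer, any time |
| 1.5 mg, 18-65 | 12 | None written |

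With a step: 12 + 6 + 6 = 24 of 36. Without: 12, all on 1.5 mg. At ages 18-65 the contrast is a step against none. Among the elderly both doses have a step, but of different kinds and over different periods.

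**2. How much of the schedule the 3.0 mg step covers.** The planned total reproduces the 100 doses in SAP 11.8.2: 3×6 + 9×5 + 4×4 + 4×3 + 4×2 + 1 = 100. Days 1-16 hold 18 + 45 + 16 = 79 of them.

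**3. Whether the exposure table supplies the count.** Table 14.6.1.4 gives number of doses, total mg and percentage of planned dose. Ignoring doses lost to the hold itself:
- 3.0 mg halved from Day 4: 100 doses taken; 18×3.0 + 82×1.5 = 177 mg; 177/300 = 59%.
- 3.0 mg halved from Day 12: 100 doses taken; 58×3.0 + 42×1.5 = 237 mg; 237/300 = 79%.
- Elderly 1.5 mg, one dose per day fewer from Day 4, read literally to Day 25: 100 − 22 = 78 doses; 78×1.5 = 117 mg; 117/150 = 78%.

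Reduction therefore lowers the percentage of planned dose, but missed doses for any reason do too. For an individual, comparing dose count with mg separates the two. Group means, medians and minima do not give the number of subjects reduced.

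**4. Whether the severity tables supply it.** Tables 14.3.1.1 and 14.3.1.4 count subjects by severity. SAP 11.6.1 counts a subject with repeated occurrences once, at maximum severity, so a recurrent severe event looks the same as a single one. The action that followed is not shown.

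**5. Whether the direction of distortion can be fixed.** It cannot, because 8.9 gives no outcome for recurrence in the 12 subjects aged 18-65 on 1.5 mg. As an illustration on assumed rates only, suppose 20% of every cell has a recurrent severe event (on 3.0 mg, within Days 1-16) and 25% of those reduced have it again and are withdrawn. Expected withdrawals on 3.0 mg are 18×0.2×0.25 = 0.9. On 1.5 mg:
- If those aged 18-65 are withdrawn at recurrence: 12×0.2 + 6×0.2×0.25 = 2.7.
- If they are held again and none is withdrawn: 6×0.2×0.25 = 0.3.

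With identical underlying tolerability, the row could read 2.7 against 0.9 or 0.3 against 0.9. Across assumed recurrence rates of 10% to 30%, the first case runs from 1.35 against 0.45 to 4.05 against 1.35, and the second from 0.15 against 0.45 to 0.45 against 1.35. If every reduced subject has the event again (20% rate), the two cases give 3.6 against 3.6 and 1.2 against 3.6. These figures show only that the sign depends on an unwritten rule.

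**The case against.** The strongest reply has four parts.

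First, the SAP delivers what the protocol asks for. Protocol 15.9 specifies AEs, serious AEs and AEs leading to discontinuation, and SAP 11.6.1 adds severity and relationship. This stands: the SAP does not depart from the protocol here, and the gap is in what the endpoint itself captures.

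Second, summary formats are set by shells that are redacted, and SAP 11.6.1 introduces its list as including the items named. This also stands. The point rests on the visible text and table titles, and a hold or reduction row may exist in the shells.

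Third, both reduction steps require a recurrent severe event. If events are graded as 8.9 requires, the count of subjects with a severe TEAE is a ceiling on the number reduced, defined alike in every group. With 36 subjects, Listings 16.2.1.2 and 16.2.7.1 would allow a count by hand. Both are true, but a ceiling is not a count, and a stated comparison between doses should not depend on readers assembling it from listings.

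Fourth, a reader might infer that subjects aged 18-65 on 1.5 mg must be withdrawn at recurrence, so that the withdrawal row flatters 3.0 mg. The documents do not support that. Section 8.9 is silent on this case, its hold wording is general, the withdrawal reasons in Protocol 6.3 are the same for all groups, and 3.0 mg subjects are still withdrawn if the event recurs after reduction.

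**Conclusion.** The point holds as a minor gap in the tolerability summary. In the visible plan, withdrawal is the only drug action tabulated, while 24 of 36 planned subjects have a written reduction step before withdrawal and the other 12, all aged 18-65 on 1.5 mg, do not. The withdrawal row alone is therefore an incomplete basis for comparing the doses, most clearly at ages 18-65. Cells are small enough for single subjects to matter: one is 1/18 = 5.6% of a dose group, 1/12 = 8.3% of an 18-65 cell and 1/6 = 16.7% of an elderly cell.

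It would go too far to call the withdrawal row wrong or biased in a known direction. It correctly reports withdrawals under each group's rules. The study is exploratory with no hypothesis test planned, 8.9 does not expect modifications to be needed, and how many will occur is unknown. The conclusion assumes planned cell sizes and that the redacted shells contain no hold or reduction row.

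**What to change.** In SAP 11.6.1 and Table 14.3.1.1 add two rows beside withdrawal, by dose group and age group:
- n (%) of subjects with a TEAE leading to a dose hold or skip;
- n (%) of subjects with a TEAE leading to a dose reduction under Protocol 8.9.

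The rows are not exclusive, since a 3.0 mg subject is held before being reduced, and they should not be merged with withdrawal into a composite. Derive them from the action taken for each AE (Protocol 13.2.2 and 15.9.4) and the dosing records in Listing 16.2.1.2. The full set of action codes is not shown in the documents. If it has no hold or reduction code, use the dosing records with the AE dates.

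Footnote the table: half dose for 3.0 mg on Days 1-16; one dose per day fewer for elderly subjects on 1.5 mg; no reduction rule written for 1.5 mg at ages 18-65. If the shells already carry such rows, naming them in 11.6.1 and adding the footnote is enough.

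No change to dosing, data collection or testing is needed. The cost is a slightly longer table and a 3.0 mg result that may look less favourable.

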11.6.2 Laboratory Data

Routine biochemistry and haematology tests will be carried out at Screening and prior to discharge on days 4, 13, 17, 21 and 26. Urinalysis will be performed at Screening and Day 26.

The laboratory parameters required for this study are listed in section 9.2.1.

Laboratory data listings will be presented in two ways:

- Out of range values - any values that fall outside of the normal/alert ranges (presented in listing format within the data summaries)
- All laboratory data (including physician’s review (Normal, Abnormal-NCS, Abnormal-CS)) with any out of range values flagged (presented within the data listings).

Descriptive statistics (N, n, mean, SD, minimum, median and maximum) of absolute and change from baseline (Screening) biochemistry and haematology parameters at each time point up to and including Day 26 will be tabulated by dose group and age group.

Laboratory data will be listed and summarised using the Safety Set.

11.6.3 Vital Signs

Supine blood pressure, pulse rate and oral temperature will be taken as follows: Screening; Day -1; Days 1, 2 and 3 pre-first dose and 3h post-last dose; Days 4, 13, 17, 21, 25 pre-first dose; Day 12, 16, 20 and 24 3h post-last dose; Day 25 24h.

Vital signs parameters (supine systolic and diastolic blood pressure and pulse rate and oral temperature) will be listed with any out of normal range values (see Appendix 1) flagged (flag ‘H’ or ‘L’ appended to relevant result). Descriptive statistics (N, n, mean, SD, minimum, median and maximum) of absolute and change from baseline (Day 1, pre-first dose) at each time point up to and including Day 25, 24h will be tabulated by dose group and age group.

Vital signs data will be summarised and listed using the Safety Set.

11.6.4 Electrocardiogram

11.6.4.1 12-Lead ECG

12-lead ECGs will be performed in triplicate as follows: Screening; Day -1; Days 4, 13, 17 and 21 pre-first dose; Day 26.

12-lead ECG parameters (heart rate, PR interval, QRS duration, QT interval and QTcF interval) will be listed with any out of normal range values (see Appendix 16.1) flagged (flag 'H' or 'L' appended to relevant result). The ECG findings (i.e. parameter values as well as morphologic findings (rhythm, conduction, evidence of MI, ST segments, T waves etc.)) will also be assessed by a physician as either 'normal' or 'abnormal' with comments on abnormal results also presented.

Descriptive statistics (N, n, mean, SD, minimum, median and maximum) of absolute and change from baseline (Day -1) values at each time point up to and including Day 26, will be tabulated by dose group. The mean of the triplicate recordings at each time point will be calculated for use in the summary tables. Any ECG traces that are determined to contain a technical error/interference will not be included in the calculation of mean values. If an ECG recording is repeated, all 3 of the original triplicate recordings (or whatever number of ECGs are free of technical errors) and the repeat recording(s) will be included in the calculation of the mean, provided that the original and repeat recordings are within 5 minutes of each other. Otherwise, the mean will be derived separately for the original and repeat recordings and the last mean value prior to dosing will be used for the summary tables.

12-lead ECG data will be listed and summarised using the Safety Set.

11.6.4.2 Holter Monitoring

The ECG extraction time points will be from extraction windows which precede the PK blood draws. ECG parameters (heart rate, PR interval, QRS duration, QT interval and QTcF interval) will be extracted in triplicate from Holter recordings on Day 1 and Day 25 at 30 and 15 minutes prior to the first dose and at 0.5h, 1h, 2h, 3h, 4h, 6h, 8h, 12h and 24h post dose.

The extracted ECG parameters will be listed with any out of normal range values (see Appendix 1) flagged (flag 'H' or 'L' appended to relevant result). The ECG results will also be assessed as either 'normal' or 'abnormal' with comments on abnormal results also presented.

The mean of the triplicate recordings at each time point will be calculated for use in the summary tables and plots. Any ECG traces that are determined to contain a technical error will not be included in the calculation of the mean values. At each time point, the mean value will be derived from all ECGs (generally three) that are free of technical errors. Descriptive statistics (N, n, mean, SD, minimum, median and maximum) of absolute and change from baseline (see definition, Section 5) values on Day 1 and Day 25 at each time point up to 24h, will be tabulated for each dose group and age group. The change from baseline ECG results will also be plotted over time by dose group and age group.

In addition, frequencies of QTcF data will be calculated according to the following categories:

For absolute values:

- QTcF > 450 mSec
- QTcF > 480 mSec
- QTcF > 500 mSec

For change from baseline:

- QTcF increase > 30 mSec
- QTcF increase > 60 mSec.

The presence of outliers will be explored for heart rate, PR interval, QRS duration, QT interval and QTcF interval). The outlier analysis will use the time-averaged baseline (see definition, Section 5) and compare that baseline value to each of the individual on-treatment ECG time point values. Outliers are defined as follows for this analysis:

- Heart rate: A value for a subject will be considered to be an outlier at a pre-defined post dose time point if the heart rate measurement at that time point is <50 bpm and the measure is at least a 25% decrease from the subject's baseline mean heart rate (i.e., a bradycardic event) or if the heart rate measurement at the pre-defined post dose time point is >100 bpm and the measure is at least a 25% increase from the baseline mean heart rate (i.e., a tachycardic event).
- PR interval: A value for a subject will be considered to be an outlier at a pre-defined post dose time point if the PR interval at that pre-defined post dose time point is >200 mSec and it is at least a 25% increase from the subject's baseline mean PR interval.
- QRS duration: A value for a subject will be considered to be an outlier at a pre-defined post dose time point if the QRS duration at that pre-defined post dose time point is >100 mSec and it is at least a 25% increase from the subject's baseline mean QRS duration.
- QT interval: A value for a subject will be considered to be an outlier at a pre-defined post dose time point if the QT interval at that pre-defined post dose time point is >500 mSec and the subject's baseline mean QT interval is \leq 500 mSec.
- QTcF interval: A value for a subject will be considered to be an outlier at a pre-defined post dose time point if the QTcF interval at that pre-defined post dose time point is >500 mSec and the subject's baseline mean QTcF interval is \leq 500 mSec. Outlier values will also be presented if the QTcF interval at a pre-defined post dose time point is >480 mSec when the subject's baseline mean QTcF interval is \leq 480 mSec and when a pre-defined post dose time point is >450 mSec when the subject's baseline mean QTcF interval is \leq 450 mSec. Subjects will be included on a 'worst case' basis, i.e. if a subject has a baseline \leq 450 mSec and has a post dose value of >500 mSec, the subject will be counted in the >500 mSec category only.

The number of events and number (%) of subjects with at least one outlier will be summarized on Day 1 and Day 25 by dose group and age group for each ECG parameter. For heart rate, separate summaries will be provided for bradycardic events (i.e., decreases) and tachycardic events (i.e. increases).

Holter ECG data will be listed for the Safety Set and summarised using the ECG Set.

